**FIGURES**

Figure 1: Schematic Overview of the Study .....	35
Figure 2: Schematic Overview Study Treatment Administration .....	43

Applicable Section(s)	Description of Change(s)
Synopsis, Primary Objective, Hypothesis, and Overview of Study Design; 1.3 Overall Rationale for the Study; 2.1 Objectives, Primary Objective; 2.2 Hypothesis; 3.1 Overview of Study Design; Figure 1; Table 3; 3.2 Study Design Rationale, 1); 4.1 Inclusion Criteria #4; 9.1.2 Screening Phase; 11.2 Sample size determination; 11.3.1 Primary Efficacy Endpoint; 11.9 Interim analysis	Stage 2 will allow for enrollment of subjects with all levels of CD38 expression. Changed CD38 expression level for subset of Stage 2 to <50% throughout. Removed CD38 positive subjects from text throughout.
Synopsis, Subject Population; 4.1 Inclusion Criteria #2, MCL	Changed "ibrutinib" to "Bruton's tyrosine kinase (BTK) inhibitor"
4.2 Exclusion Criteria #3	Subject history of malignancy was reduced to be less strict from 5 years before screening period to 3 years. The minimal risk of recurrence was reduced from 3 years to 2 years.
4.2 Exclusion Criteria #5	Subjects with a history of Hepatitis C should not be excluded if the viral load becomes negative with modern therapy.
4.2 Exclusion Criteria #10	Added emergent use of steroids at screening stage (100 mg prednisone per day or equivalent for up to 7 days).
Rationale: Due to risk of daratumumab interference with IAT testing, text was removed from Prohibitions and Restrictions and added to Sec 9.5 Safety Evaluations to be consistent to other daratumumab protocols.	
4.3 Prohibitions and Restrictions	Removed the text pertaining to daratumumab interference with indirect antiglobulin testing (IAT) from here as this information is provided in Section 9.5 Safety Evaluations.
9.5 Safety Evaluations	Updated text on daratumumab interference with indirect antiglobulin testing (IAT) to align with other daratumumab protocols.

Applicable Section(s)	Description of Change(s)
	
Rationale: Optional endoscopy at baseline added as CRs must be confirmed with endoscopy if the lymphoma originated from or involved the GI tract at diagnosis.

Table 1 Time and Events Schedule Overview; 9.2.1.5 Endoscopy (new)	Endoscopy added. New section added: CRs must be confirmed with endoscopy examination if the lymphoma originated from or involved the GI tract at diagnosis.
	
Rationale: To reflect current practice, updated management of infusion-related reactions section to indicate that the infusion will be paused (not interrupted or slowed down) if an infusion-related reaction occurs.

6.3.3 Management of Infusion-Related Reactions	If an infusion-related reaction develops, then the infusion should be paused temporarily <del>interrupted or slowed down</del> .
	
Rationale: Removal of the term “legally acceptable representative” to address IRB concerns that for those adults who lack capacity to consent should be excluded.

4.1 Inclusion Criteria #10, 9.5 Safety Evaluations (Adverse Events); 10.2 Discontinuation of Study Treatment; 15.2.3 Informed Consent; 16.2.4 Privacy of Personal Data	Removal of “legally acceptable representative” throughout the protocol.
	
Rationale: Beta 2 microglobulin (β2M) was added because it is an important lymphoma biomarker for tumor burden as well as prognosis.

Table 1 Time and Events Schedule Overview; 9.5 Safety Evaluations; 11.3.1 Primary Efficacy Endpoint	Beta 2 microglobulin was added to the Time and Events Schedule and safety analyses. Statistical methods for beta 2 microglobulin were added.

---

Applicable Section(s)	Description of Change(s)
-----------------------	--------------------------

---

**Rationale:** Minor errors were noted

---

Throughout the protocol	Minor grammatical, formatting, or spelling changes were made.
-------------------------	---

---

Progression-free survival and OS will be analyzed using the Kaplan-Meier method, and the comparison between the above- and below-threshold subpopulations will be made using log-rank test and Cox regression.

R-Hyper-CVAD	rituximab + hyper-CVAD
R-ICE	rituximab, ifosfamide, carboplatin, and etoposide
SAE	serious adverse event
SIPPM	Site Investigational Product Procedures Manual (or equivalent document)
ULN	upper limit of normal
VGPR	very good partial response
VR-CAP	bortezomib, rituximab, cyclophosphamide, doxorubicin, and prednisone

fulfill the eligibility criteria, including tumors with  $\geq 50\%$  cells CD38 positive for Stage 1 and tumors  $< 50\%$  cells CD38 positive or  $\geq 50\%$  cells CD38 positive for Stage 2, will be considered for participation in the study. An ICF for CD38 screening only may be obtained separately from the full study ICF.

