#### **9.2.2.2. Major Secondary Endpoints**

Duration of response (DoR) will be duration from the date of the initial documentation of a response to the date of first documented evidence of PD (or relapse for subjects who experience CR). For those subjects who are still without progression/relapse, DoR will be censored at the last adequate tumor assessment.

PFS is defined as the duration from the date of the first daratumumab dose to the date of progression/relapse or death, whichever comes first. For those subjects who are still alive without progression/relapse, PFS will be censored at the last adequate tumor assessment.

Overall survival (OS) is defined as the duration from the date of the first daratumumab dose to the date of death. For those subjects who are still alive without progression/relapse, OS will be censored at the last date known to be alive.

Time to response is defined as the duration from the date of the first dose of daratumumab to the earliest date that a response (CR/PR) is first documented. For non-responders, it will be censored at the date of progressive disease/relapse or the date of the last adequate disease assessment, whichever comes first.

additional sampling is required. Procedures for sample collection, preparation, identification, storage, and shipment will be provided in the Laboratory Manual or equivalent document.

Additionally, blood samples should also be collected at the final visit from subjects who are discontinued from treatment. Subjects who discontinue treatment will also be asked to return for immunogenicity evaluation during the Follow-up Phase.

A blood sample should be drawn, if possible, for determination of antibodies to daratumumab any time an infusion reaction is observed or reported during the study. Daratumumab serum concentration will also be determined from the same infusion reaction sample for the purpose of interpreting immunogenicity data. These samples will be stored and evaluated if deemed necessary. If the infusion reaction results in treatment discontinuation, then subjects should undergo all scheduled safety and efficacy evaluations. Samples collected for the analysis of daratumumab immunogenicity/serum concentration may additionally be used to evaluate safety or efficacy aspects that address concerns arising during or after the study period or for the evaluation of relevant biomarkers by the sponsor or sponsor's designee.

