Alternatively, if the futility criteria are not met and if supported by the totality of the Stage 1 data, Stage 2 for that NHL subtype may be opened for accrual. If the required number of responses is observed prior to completion of enrollment in Stage 1, Stage 2 may be opened immediately upon completion of enrollment to Stage 1, if supported by the totality of data.

Stage 2, if opened, is designed to further evaluate safety and efficacy as well as to determine a threshold for CD38 expression that is associated with enhanced daratumumab activity. Supported by the preliminary activity observed in Stage 1, Stage 2 will enroll any subject in each NHL subtype. To mitigate the possibility that a low response may be observed due to low levels of

CD38 expression in enrolled subjects, the number of Stage 2 subjects with CD38 expression level <50% will be capped within each NHL subtype.

The target number of subjects in each stage by CD38 expression level is shown in table below.

Type of NHL	Number of Subjects			Overall Total
	Stage 1 CD38 expression level ^b ≥50%	Stage 2 (optional)		
		CD38 expression level ^a <50%	CD38 expression level ^b ≥50%	
MCL	20	≤30	≥50	100
DLBCL	15	≤20	≥20	55
FL	15	≤20	≥20	55

DLBCL=diffuse large B cell lymphoma ; FL=follicular lymphoma; MCL= mantle cell lymphoma

a. These subjects have tumors where <50% of the cells are positive for CD38 by immunohistochemistry.

[figure not shown]
b. These subjects have tumors where ≥50% of the cells are positive for CD38 by immunohistochemistry.

Subject participation will include a Screening Phase, a Treatment Phase, and a Follow-up Phase.

The Screening Phase will be up to 28 days prior to Cycle 1, Day 1. Prior to enrollment, subjects are required to provide tumor tissue to determine CD38 expression level by immunohistochemistry (IHC) at a central laboratory. An additional fresh biopsy should be obtained whenever possible even if an archival sample is provided.

The Treatment Phase will extend from Cycle 1, Day 1 until study drug discontinuation. After first dose, disease evaluations will occur every 8 weeks for the first 3 evaluations, then every 16 weeks for the next two evaluations and then every 24 weeks thereafter. Subjects will be treated until disease progression, unacceptable toxicity, or other reasons as listed in the protocol.

A schematic overview of the dosing schedule is presented as follows.

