1.2. Sample Size Justification

Within each subtype of NHL, a biomarker adaptive threshold design (Jiang 2007)² is to be utilized, which allows identification of a biomarker threshold based on data analysis in parallel with the statistical testing of the ORR for proof-of-concept. That is, the proof-of-concept could be established either in the overall population or in the subpopulation of subjects as identified by the biomarker (CD38 expression level) threshold. In order to provide an early futility check within each NHL subtype, a two-stage procedure is also incorporated.

Given that there are two potential pathways for proof-of-concept and the inherent multiple testing issues associated with the selection of the biomarker threshold, per the recommendation by Jiang (2007)², the powering for MCL will be based on the overall population with an overall alpha of 0.04, which preserves the power of the overall test while providing a reasonable power against a strong subset effect at the same time with the remaining alpha of 0.01. Since further randomized Phase 2 proof-of-concept studies in combination with other agents are likely required for DLBCL and FL, an alpha of 0.05 is used for the overall population in these two subtypes.

In Stage 1, a total of 50 subjects will be enrolled for all 3 NHL types combined. In Stage 2, a maximum of 160 subjects may be enrolled if all three tumor types are expanded, bringing the maximal sample size to 210 with all tumor types combined.

For MCL, the null hypothesis is that the ORR is at most 20%, and the alternative hypothesis is that the ORR is at least 35% for all subjects, or at least 40% for those subjects whose CD38 expression level is above a to-be-determined level. These are based on the fact that some recent approvals in previously treated MCL were based on an ORR of approximately 31% for bortezomib and 26% for lenalidomide. Up to 100 MCL subjects with positive CD38 expression may be enrolled. Seventy (70) of those must have tumors with 50% or more cells positive for CD38 expression at baseline in order to rule out that any lack of activity is mostly due to low CD38 expression level in the enrolled subjects.

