subjects will have tumors where $\geq 50\%$ of cells are CD38 positive. The sample size will provide approximately 80% power to reject the null hypothesis for the overall population with a one-sided significance level of 0.05.

For FL, Stage 1 will accrue 15 subjects with tumors where $\geq 50\%$ of cells are CD38 positive. If the futility criteria are met (at most 6 responses overall), no further expansion is planned. Otherwise, an additional 40 subjects will be enrolled to Stage 2; at least 20 of these subjects will have tumors where $\geq 50\%$ of cells are CD38 positive. The sample size will provide approximately 80% power to reject the null hypothesis for the overall population with a one-sided significance level of 0.05.

At the end of the study, all available data for each particular NHL subtype will be analyzed to determine a CD38 expression threshold for that subtype, which will be used to define an enriched population, via statistical inference.

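### PFS and OS are compared across a CD38 threshold found in the same subjects; the visible text adjusts for that search only in the ORR test (minor, conditional on the part of protocol Section 11 not shown)

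*Protocol*

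**What the plan says.** The protocol's sentence on PFS and OS analysis, printed after the amendment table, gives Kaplan-Meier estimation and then says that "the comparison between the above- and below-threshold subpopulations will be made using log-rank test and Cox regression". It names no test level and no adjustment.

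The threshold comes from the same study. SAP 1.1 gives as an aim of Stage 2 "to determine a threshold for CD38 expression that is associated with enhanced daratumumab activity". SAP 1.2 says that the design "allows identification of a biomarker threshold based on data analysis in parallel with the statistical testing of the ORR", and that, once follow-up is complete, "all available data for each particular NHL subtype will be analyzed to determine a CD38 expression threshold for that subtype". The result is to define an enriched population.

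SAP 1.2 recognises the "inherent multiple testing issues associated with the selection of the biomarker threshold". Its remedy concerns the proof-of-concept test on ORR. In MCL, 0.04 goes to the overall population and 0.01 to the subset. For DLBCL and FL, "an alpha of 0.05 is used for the overall population in these two subtypes".

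The SAP available is for the interim futility analyses (SAP 1). It treats time-to-event data descriptively by Kaplan-Meier (SAP 2.9) and contains no comparison across the threshold (SAP 4.3.1, 4.3.2). The amendment table shows that protocol Sections 11.2, 11.3.1 and 11.9 exist, but their text is not available.

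**The concern.** A log-rank p-value and a Cox hazard ratio have their usual meaning when the groups are fixed without reference to outcome. Here the groups are formed by a search through the outcome data of the subjects who are then compared. If the search maximises the response contrast, it tends to place responders above the cut, and any link between response and PFS carries the chance imbalance into the PFS comparison.

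Part of that link is built in. In protocol 9.2.2.2, "PFS is defined as the duration from the date of the first daratumumab dose to the date of progression/relapse or death", and in SAP 1.1 "disease evaluations will occur every 8 weeks for the first 3 evaluations". A subject whose response is documented at a scheduled evaluation is therefore progression-free to week 8 at least.

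At stake is how the threshold is read. A nominally significant PFS or OS difference could pass as independent support for a cut that was chosen to look good in the same subjects.

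**Working it through.** **The plan's own figure.** The documents give no error rate for the PFS/OS comparison. The nearest figure is the MCL power for ORR, which checks the design inputs. With 20 + 80 subjects, Stage 2 opened at 5 or more responses and rejection at 28 or more of 100, P(reject) = Σ(x=5..20) Bin(x; 20, p) × P[Bin(80, p) ≥ 28 − x]. This gives 84.7% at p = 0.35 and 0.026 at p = 0.20 (a cut of 27 would give 0.041). The stated approximate 85% at one-sided 0.04 is reproduced.

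**Inputs from the documents.** Stage sizes, opening rules and caps on CD38-low subjects (SAP 1.1); alternative ORRs of 35%, 30% and 50% for MCL, DLBCL and FL (SAP 1.2); follow-up to 18 months after the last first dose (protocol 9.1.4); evaluation schedule (SAP 1.1).

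**Assumptions, not in the documents.** CD38 unrelated to response, PFS or OS. CD38 uniform within the <50% and ≥50% bands, with the CD38-low cap filled. Exponential times, non-responder median PFS 3 months, responder hazard ratio (HR) 0.3 unless stated. Test level two-sided 5%, borrowed from the two-sided 95% intervals in SAP 4.1.1.

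**Selection rule, central case (assumed).** For cuts c = 20, 30, ..., 80%:

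z(c) = (ORR above − ORR below) / √[p(1 − p)(1/n above + 1/n below)], where p is the pooled ORR.

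Take the c with the largest z, compute the log-rank Z there and reject if |Z| > 1.96.

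**Results**, as a percentage of simulated cohorts that open Stage 2 (20,000 per cell, 10,000 for the every-value row; Monte Carlo SE 0.2-0.3 points). Ranges span the three subtypes and, in some rows, further sensitivity settings. With a valid test the columns would read 5 and 2.5.

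| Setting | Two-sided | Favours above |
|---|---|---|
| PFS, fixed 50% cut | 5.3-5.7 | 3.4-3.8 |
| PFS, central rule | 7.5-8.5 | 7.0-7.7 |
| PFS, cuts 50-90% only | 6.2-6.9 | 5.3-5.5 |
| PFS, every observed value a candidate | 10.0-10.4 | 9.5-10.0 |
| PFS, HR 0.5 | 5.6-7.9 | 4.0-6.9 |
| PFS, HR 0.7 | 6.1-6.3 | 4.4-4.6 |
| PFS, HR 1 | 5.5-6.1 | 3.1-3.2 |
| PFS, evaluation schedule only, no benefit after response | 5.8-6.7 | 4.0-5.6 |
| Same, fixed cut | 5.0-5.5 | 2.8-3.4 |
| OS, HR 0.3 | 6.5-7.5 | 5.6-6.9 |
| OS, fixed cut | 5.1-5.8 | 3.1-3.7 |

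**Excess over the fixed cut.** A separately coded run of the central rule gave 7.2, 8.0 and 8.0% (MCL, DLBCL, FL) against 5.3, 5.4 and 5.7%, so 7.2 − 5.3 = 1.9, 8.0 − 5.4 = 2.6 and 8.0 − 5.7 = 2.3 points. At HR 0.5 with a one-sample rule over deciles: 6.83 − 5.58 = 1.3, 7.38 − 5.71 = 1.7 and 7.81 − 5.51 = 2.3 points.

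**Source of the excess.** Without the Stage 1 opening rule, the search gives 7.2-7.3% against 5.2-5.6% with the fixed cut. The search is therefore the main cause. The opening rule adds a little even to a fixed cut, because Stage 1 subjects all lie at or above 50% and the cohort continues only if enough of them respond.

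**Other one-directional rules at HR 0.3.** Rules using 20-80% quantiles give 6.7-8.0%, with 83-90% of rejections favouring above. Choosing the highest ORR above the cut, or deciles from 50% upward, gives 5.1-7.1% (75-91%). If the whole population is also a candidate, 38-55% of cohorts yield no comparison and 5.7-8.3% reject (98-100%).

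**Size of the estimate.** With a true above/below HR of 1, the median apparent Cox PFS HR under the central rule is 0.85-0.89, against 0.97-0.99 with the fixed cut.

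**Check of a remedy.** A permutation test that shuffles CD38 within stage and repeats the search each time rejects in 5.0, 4.6 and 5.1%. The nominal test in the same runs gave 7.8, 8.1 and 6.8% (2,400 cohorts per subtype, SE about 0.4 points).

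**The case against.** The strongest reply is that the gap may lie in what can be seen and not in the plan. A one-sentence summary is not where a selection correction would normally be written, and Section 11 is mostly unavailable. The authors plainly knew of the problem: they name it, cite a published adaptive-threshold procedure and say that the threshold is to be set by statistical inference. This stands. A reader might infer that the plan has no adjustment for PFS and OS; the documents do not support that, only that none is visible.

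The second reply is that the figures are mostly assumption. This also stands. The selection rule, the cut grid, the responder HR and the test level are not in the documents, and selection on response is itself inferred. A reader might take 7-8% and nine in ten as the error rate of this plan, but those figures belong to particular rules at HR 0.3. The only mechanism tied to the documents, the evaluation schedule, gives about 1 point. Nor is all excess over 5% selection bias: at HR 1, where response carries no information on PFS, the one-sample decile rule still gives 6.1-7.3%.

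A two-directional search gives 8.8-14.5% with no clear direction (49-64% favouring above), but it does not fit an aim of finding enhanced activity.

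The third reply is low consequence. PFS and OS are secondary, and no visible decision uses the test. If a subtype stops for futility, the interim SAP has no threshold comparison at all. This settles the severity. It does not remove the point, because the protocol sentence as written would still produce an unadjusted p-value and HR.

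**Conclusion.** The point holds as a minor one, conditional on Section 11. On the visible text, PFS and OS are tested across a threshold derived from the same subjects, and selection is allowed for only in the ORR test. If the cut is chosen on response and responders progress later, the comparison leans towards the above-threshold group even for an irrelevant marker.

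For one-directional rules at a responder HR of 0.3 and the alternative ORRs, a nominal two-sided 5% PFS log-rank test rejects in about 5-10% of opened cohorts, and about 75-100% of the rejections favour above. The largest two-sample z over cuts of 20-80% gives about 7-9% and about nine in ten; cuts of 50-90% give about 6-7%. The fixed 50% cut gives 5-6%. The excess shrinks to about 1-2 points at HR 0.5 and to essentially none at HR 1, and some rules would give no comparison in many cohorts. Nothing here bears on the error rate of the primary ORR test.

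**What to change.** If Section 11 already adjusts the PFS/OS comparison, add a cross-reference to the protocol sentence; nothing more is needed.

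Otherwise, in that sentence and in the final SAP, present the above- and below-threshold Kaplan-Meier curves and HRs as descriptive and exploratory, without p-values. State that the threshold was chosen in the same subjects, so the HR is likely to be optimistic. This agrees with the descriptive approach of SAP 2.9. The cost is one sentence and the nominal p-value.

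Only if a p-value is wanted, state the threshold-selection rule and use the within-stage permutation test, with the full search repeated in every permutation. Shuffling within stage is needed because Stage 1 admits only subjects at or above 50% and is conditioned on passing its response hurdle. The cost is some computing time and less favourable p-values. Neither route needs extra patients.

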### 9.1.3. Treatment Phase

Details of the procedures performed during the Treatment Phase are outlined in the [Table 1](#). The start of each cycle should be scheduled relative to Cycle 1 Day 1 and should not change if visits have shifted within the allowed window. Subjects will be closely monitored for adverse events, laboratory abnormalities, and clinical response. Clinical evaluations and laboratory studies may be repeated more frequently, if clinically indicated. If disease progression is diagnosed, then the subject will discontinue study treatment, complete the End-of-Treatment Visit, and enter the Follow-up Phase.

#### End-of-Treatment Visits

Unless a subject withdraws consent for study participation or is lost to follow up, an End-of-Treatment Visit is to occur within 30 days (+7 day window) after the last dose of all study treatments. Every effort should be made to conduct the End-of-Treatment Visit before the subject starts subsequent treatment. If a subject is unable to return to the site for the End-of-Treatment Visit, then the subject should be contacted to collect information on adverse events and concomitant medications that occur up to 30 days after the last dose of study treatment. Additional information on reporting of adverse events is presented in [Section 12](#).

### 9.1.4. Follow-up Phase

The Follow-up Phase will begin once a subject discontinues study treatment. Subjects who discontinue before disease progression (for other reasons such as an AE) must continue to have their regularly scheduled scans according to the [Table 1](#) until confirmed PD, death, the start of a new anticancer therapy, withdrawal of consent, lost to follow up, or the end of the study for that NHL subtype. After disease progression is documented, follow-up will occur at least every 16 weeks ( $\pm 2$  weeks). Subsequent anticancer therapy, second primary malignancies, and survival status will be recorded.

If the information is obtained via telephone contact, written documentation of the communication must be available for review in the source documents. If the subject has died, the date and cause of death will be collected and documented in the eCRF.

The end of the cohort for each NHL subtype is defined as 18 months after the last subject in the particular NHL subtype receives the first dose of daratumumab. After completion of an NHL subtype, the sponsor will ensure that subjects who are currently on treatment and receiving benefit, as determined by the investigator, will continue to receive daratumumab. The end of the study is defined as the completion of all three NHL subtypes.

not measurable but are thought to represent lymphoma. In addition, if more than 6 sites of disease are measurable, these other sites of measurable disease may be included as assessable disease.

